## 4. STUDY DESIGN

### 4.1. Overall Design

This is a Phase 2a, single-blind, randomized, placebo-controlled, parallel-group, multiple-dose study to assess the PK, PD, and safety of brensocatib 10, 25, and 40 mg QD in participants with CF. Following review of safety and PK data by the SRC and provided that the SRC deems it appropriate to administer the next higher dose, an additional cohort of participants will receive brensocatib 65 mg QD on the same schedule as the previous cohorts. A tablet formulation of brensocatib 65 mg is not yet available; therefore, participants randomly assigned to the 65 mg dose cohort will receive the following:

- 1 tablet of brensocatib 25 mg QD plus 1 tablet of brensocatib 40 mg QD × 28 days
- OR
- 2 tablets of matching placebo QD × 28 days

[Section 6.3](#) describes the procedures for blinding the study drug.

Overall, the study will enroll approximately 25 to 34 participants. The first three brensocatib dose cohorts (10 mg, 25 mg, and 40 mg QD) will enroll approximately 7 participants each, and the placebo cohort will enroll approximately 4 participants.

For many patients with CF, CFTR modulators are the cornerstone of their treatment ([van der Meer et al., 2021](#)). The proportion of patients prescribed a CFTR modulator has expanded over time, with approximately only 14% of the eligible population not prescribed a CFTR modulator ([CF Foundation Registry, 2020](#)). For the active treatment dose cohorts, there will be 2 strata: approximately 5 participants who have previously received and will continue to receive CFTR modulators as concomitant medication (CFTR modulator stratum), and approximately 2 participants who have either never previously received CFTR modulators or have not been administered CFTR modulators within 30 days prior to Screening (visit 1) and will not receive CFTR modulators during the study (non-modulator stratum). For the placebo cohort, approximately 3 participants will be randomized into the CFTR modulator stratum and 1 participant in the non-modulator stratum.

As described in [Table 1](#), each cohort will enroll participants in a 5:1 ratio (active : placebo) for the CFTR modulator stratum. For the non-modulator stratum, approximately 6 participants will be randomized to receive active treatment (10 mg, 25 mg, and 40 mg brensocatib) and approximately 1 participant to placebo.

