## **6. INVESTIGATIONAL PRODUCT AND CONCOMMITANT THERAPY**

Investigational product is defined as any investigational intervention(s), marketed product(s), placebo, or medical device(s) intended to be administered to a study participant according to the study protocol. In this protocol, the terms “investigational product” and “study drug” are interchangeable.

Brensocatib film-coated tablets are round, biconvex, brown, film-coated tablets containing the equivalent of 10 mg, 25 mg, and 40 mg of brensocatib (INS1007) drug substance and to be administered orally QD. Each film-coated tablet contains active ingredient of brensocatib drug substance and compendial ingredients: microcrystalline cellulose, dibasic calcium phosphate dihydrate, sodium starch glycolate, silicon dioxide, and glyceryl behenate.

Participants will be assigned to receive brensocatib 10, 25, or 40 mg QD or placebo QD for 28 days. They will be randomly assigned to a dosing cohort with 10 participants receiving active drug and 2 participants receiving placebo (12 participants per cohort). Insmmed will provide sites with the investigational products as described in [Table 2](#).

Participants will receive the same number of tablets each day to maintain the blind.

If the 65 mg is to be assessed, participants in this cohort will receive 65 mg QD (25 mg + 40 mg tablets) or matching placebo tablets on the same schedule as the previous cohorts.

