### 9.2. Sample Size Determination

Overall, the study will enroll approximately 25 to 34 participants. The 10 mg, 25 mg, and 40 mg cohorts will enroll approximately 7 participants each, and the placebo cohort will enroll approximately 4 participants. For the active treatment cohorts, there will be 2 strata: approximately 5 participants who have previously received and will continue to receive CFTR modulators as concomitant medication and 2 participants who have either never previously received CFTR modulators or have not been administered CFTR modulators within 30 days prior to Screening (visit 1) and will not receive CFTR modulators during the study (non-modulator stratum). For the placebo cohort, approximately 3 participants will be randomized into the CFTR modulator stratum and 1 participant in the non-modulator stratum.

Each cohort will enroll participants in a 5:1 ratio (active : placebo) for the on CFTR modulator stratum. For the non-modulator stratum, approximately 6 participants will be randomized to receive active treatment (10 mg, 25 mg and 40 mg brensocatib) and 1 participant to placebo.

If there are no safety issues observed in the first 3 dose cohorts, a 65 mg dose cohort will be similarly randomized: 7 participants (5 participants CFTR modulator and 2 participants non-modulator stratum) in active treatment and 2 participants in placebo (1 participant each in the CFTR modulator and non-modulator strata), increasing the sample size from approximately 25 to 34 participants.

A formal sample size calculation has not been performed. The number of participants has been chosen based on feasibility, as is typical and standard for such multiple ascending doses study designs and is considered sufficient to meet the study objectives.

AUC0-24 and Cmax will be summarized by dose group and by dose group within each stratum (CFTR modulator and non-modulator) using the GM. The precision, as measured by the width of CIs, for these GMs will depend on the observed variability and sample size. The following tables present descriptions of 95% CIs for a range of possible values of CV(%) of the GM. [Table 5](#) presents participants treated with brensocatib per dose group (N=10 and N=7), and [Table 6](#) presents participants treated with brensocatib per stratum (N=5) (CFTR modulator) within dose group.

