**Table 5: 95% CIs for Values of Inter-Participant CV(%) of the AUC0-24 and Cmax GM in Each Actively Treated Cohort**

N	Geometric CV(%)	Geometric Mean 95% CI LL	Geometric Mean 95% CI UL
10	30	GM÷1.234	GM×1.234
	40	GM÷1.317	GM×1.317
	50	GM÷1.402	GM×1.402
7	30	GM÷1.312	GM×1.312
	40	GM÷1.428	GM×1.428
	50	GM÷1.548	GM×1.548

Note: Assumes N=number of participants treated with brensocatib per dose group.

CV = percent coefficient of variation, CI = confidence interval, GM = geometric mean, LL = lower limit, UL = upper limit.

**Table 6: 95% CIs for Values of Inter-Participant CV(%) of the AUC0-24 and Cmax GM for Each Stratum Within Each Actively Treated Cohort**

Geometric CV(%)	Geometric Mean 95% CI LL	Geometric Mean 95% CI UL
30	GM÷1.440	GM×1.440
40	GM÷1.613	GM×1.613
50	GM÷1.798	GM×1.798

Note: Assumes N=5 (number of participants treated with brensocatib per stratum in each dose group).

CV = percent coefficient of variation, CI = confidence interval, GM = geometric mean, LL = lower limit, UL = upper limit.

The range of values for GM CV(%) is based on the results of Day 29 AUClast and Cmax in a study of patients with NCFBE (INS1007-201) and on the results of Day 28 AUC0-24 and Cmax in a multiple-dose study of healthy volunteers (D6190C00001).

For the primary evaluation of safety, N=10 or 7 participants per brensocatib dose group provides 80% or 68% probability, respectively, to detect an AE that occurs with an incidence rate of 15%, and 90% or 80% probability, respectively, to detect an AE that occurs with an incidence rate of 21%.

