Note: Assumes N=number of participants treated with brensocatic per dose group.
gCV% = geometric coefficient of variation percentage, CI = confidence interval, GM = geometric mean, LL = lower limit, UL = upper limit.

Table 3: 95% CIs for Values of Inter-Participant gCV% of the AUC_{0-24} and C_{max} GM for Each Stratum Within Each Actively Treated Cohort

gCV%	GM 95% CI LL	GM 95% CI UL
30	GM÷1.440	GM×1.440
40	GM÷1.613	GM×1.613
50	GM÷1.798	GM×1.798

Note: Assumes N=5 (number of participants treated with brensocatic per stratum in each dose group).

The range of values for gCV% is based on the results of Day 29 AUC_{last} and C_{max} in a study of patients with non-cystic fibrosis bronchiectasis (NCFBE) (INS1007-201) and on the results of Day 28 AUC_{0-24} and C_{max} in a multiple-dose study of healthy volunteers (D6190C00001).

For the primary evaluation of safety, N=10 or 7 participants per brensocatic dose group provides 80% or 68% probability, respectively, to detect an adverse event (AE) that occurs with an incidence rate of 15%, and 90% or 80% probability, respectively, to detect an AE that occurs with an incidence rate of 21%.

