7. GENERAL STATISTICAL CONSIDERATIONS

7.1. General

Tables and figures will be provided by treatment group/dose level (10 mg, 25 mg, 40 mg, and 65 mg [if conducted] QD brensocatic, pooled placebo except for PK output). If sample sizes permit, summaries will be further stratified by CFTR modulator and non-modulator.

Treatment arm/dose levels will be presented in this stratified analysis if the number of observations is ≥ 2 . If the assignment to a stratum differs between the randomization file and the eCRF, the randomization file will prevail. In the listings, CFTR modulator use will be indicated by + for participants on CFTR modulator and by - for the non-modulator stratum following the Subject Identifier. For tables in the demographic and safety sections, also a Total column will be presented.

Descriptive statistics for continuous variables will be calculated at scheduled visits (nominal timepoints for PK) and will include the number of participants in the treatment group/dose level of the respective analysis set (N in column header of the table), the number of non-missing- observations (n), the number of observations below limit of quantification (BLQ) for PK and PD tests, arithmetic mean, standard deviation (SD), median, minimum, and maximum. For brensocatic plasma concentrations, the GM with 95% CI and gCV%, for PK parameters (except for t_{\max} and t_{last}), and PD tests, the GM and gCV% will be reported in addition. The GM will be derived by calculating the arithmetic mean of the natural log-transformed observations and then back-transforming the mean by exponentiation. The gCV% will be calculated as: $100 \times \sqrt{\exp[\text{variance of the log-transformed values}] - 1}$. GM and gCV% will only be calculated for quantifiable values above 0. For t_{\max} and t_{last} , only n, median, minimum, and maximum will be presented. For PK parameters, no descriptive statistics will be calculated when fewer than three individual PK parameter values are available. Summaries of continuous variables other than plasma concentrations that have some values recorded using approximate values (e.g., $<$ or $>$) will use the numeric part of the value in calculations. Rules for plasma concentrations BLQ or missing are given in [Section 11](#).

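### Protocol Section 6 still gives 12 participants per cohort, and the precision tables keep sample sizes that do not fit the current design

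*Protocol*

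**What the plan says.** - **Cohort size, Protocol Section 6 (opening text).** After naming 10, 25 and 40 mg and placebo, it states: "They will be randomly assigned to a dosing cohort with 10 participants receiving active drug and 2 participants receiving placebo (12 participants per cohort". The later sentence on 65 mg gives no number.
- **Cohort size elsewhere.** Protocol 4.1 says that the first three dose cohorts "will enroll approximately 7 participants each, and the placebo cohort will enroll approximately 4 participants". Section 9.2 gives the same sizes and the total: "Overall, the study will enroll approximately 25 to 34 participants". Table 1 splits each dose into 5 modulator and 2 non-modulator participants. The synopsis, Section 6.3 and SAP 4.1 to 4.3 agree.
- **Precision and AE detection.** Protocol Table 5 and SAP Table 2 give 95% CI factors for the geometric mean (GM) at N=10 and at N=7. Section 9.2 adds that "N=10 or 7 participants per brensocatib dose group provides 80% or 68% probability, respectively, to detect an AE" of 15% incidence; at 21% incidence the pair is 90% and 80%.
- **Strata.** The titles of Protocol Table 6 and SAP Table 3 claim each stratum, and the SAP note describes N=5 as the number treated "per stratum in each dose group". The text that introduces each table ties N=5 to the CFTR modulator stratum.
- **Outputs.** Protocol 9.2 and SAP 4.2 plan GMs of AUC0-24 and Cmax by dose, and by dose within both strata. SAP 7.1 reserves the interval for concentrations: "plasma concentrations, the GM with 95% CI and gCV%, for PK parameters" it lists only the GM and gCV%. It also gives no PK-parameter statistics when fewer than three values are available.

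**The concern.** Section 6 is current text on how participants are assigned, so the protocol holds two cohort sizes at once. The gap is too wide for the word approximately to cover: 36 against 25, and 2 placebo participants in every cohort against 4 shared by three cohorts.

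The N=10 rows carry no label to say that they belong to another cohort size. A reader may therefore take the more favourable of two figures as the one the trial delivers. The stratum tables invite a similar misreading: taken from title and note alone, they promise N=5 precision for non-modulator participants, of whom there are 2 per dose. Finally, the quantity used to describe precision for AUC0-24 and Cmax is not among the planned summaries of those parameters.

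**Working it through.** **1. Head count.**

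- Section 6: 10 + 2 = 12 per cohort; 3 × 12 = 36 (30 active, 6 placebo).
- Table 1 and Section 6.3, first three doses: modulator 3 × 5 + 3 placebo = 18; non-modulator 3 × 2 + 1 placebo = 7; total 25 (21 active, 4 placebo).
- With 65 mg: 25 + (5 + 2) active + 2 placebo = 34.

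The second and third lines reproduce the plan's 25 and 34. Section 6 differs from the three-cohort total by 36 − 25 = 11.

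**2. CI factors.** The inputs are N from the tables and gCV of 30, 40 and 50%. The factor is exp( t(0.975, n−1) × √ln(1+CV²) / √n ). For n=7 and CV 50%: √ln(1.25) = 0.472, t = 2.447, and 2.447 × 0.472 / 2.646 = 0.437, so the factor is exp(0.437) = 1.548, as stated.

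| N | gCV 30% | 40% | 50% | In the documents? | Planned group of this size |
|---|---|---|---|---|---|
| 10 | 1.234 | 1.317 | 1.402 | yes, matches | none |
| 7 | 1.312 | 1.428 | 1.548 | yes, matches | each dose |
| 5 | 1.440 | 1.613 | 1.798 | yes, matches | modulator stratum, per dose |
| 2 | 13.98 | 31.86 | 69.70 | no | non-modulator stratum, per dose |
| 6 | 1.361 | 1.498 | 1.642 | no | non-modulator stratum, three doses pooled |

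All nine published factors reproduce to three decimals. The last row assumes that dose-normalised values have the same gCV range and that exposure is dose proportional.

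**3. AE detection.** The probability of at least one affected participant is 1 − (1−p)^n.

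- N=10: 1 − 0.85^10 = 0.803; 1 − 0.79^10 = 0.905 (stated 80% and 90%).
- N=7: 1 − 0.85^7 = 0.679; 1 − 0.79^7 = 0.808 (stated 68% and 80%).

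The stated values agree to within a point. At 21% incidence and N=7 the figure rounds to 81%.

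**4. What is reported at n=2.** SAP 7.1 shows a stratum-by-dose group once it has 2 observations, but withholds PK-parameter statistics below 3 values. SAP 11.1.1 does the same for concentrations below 3 non-BLQ values. At the planned size, the by-dose non-modulator GM promised in Protocol 9.2 and SAP 4.2 will therefore not be calculated. What remains is the participant listing and the comparison in SAP 11.1.3, which pools doses within stratum if dose proportionality applies.

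**5. The missing interval.** Protocol 9.4.2 attaches the GM with 95% CI to concentrations and promises descriptive statistics for parameters, and SAP 7.1 follows it. The nearest substitute, in SAP 11.1.3, is optional, dose-normalised and uses 90% CIs.

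**The case against.** The strongest reply is that nothing operational depends on the stale sentence. Randomisation is specified in Section 6.3 through the IWRS, in Table 1 and in SAP 4.3; the SAP does not repeat 10 + 2; and no hypothesis, alpha or power is attached to cohort size. This stands as a limit on the consequences. It does not make two cohort sizes in one protocol acceptable.

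Several stronger readings are tempting, and the documents do not support them:

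- **The figures for the real dose-group size are missing or wrong.** They are not. Both documents print the N=7 factors and probabilities next to the N=10 ones.
- **The plan claims 90% detection at 21% incidence for this trial.** That figure is tied to N=10. At N=7 the 90% point is 1 − 0.1^(1/7) = 28%, but the plan says nothing to the contrary.
- **Non-modulator precision is stated as 1.44 to 1.80 when it is really 14 to 70.** No precision is stated for that stratum. The introducing text limits N=5 to modulator participants, and the rule of three values means that an interval from two values would not be reported.
- **The non-modulator stratum is the one of most interest.** Neither document says so. The protocol makes it small because only about 14% of eligible patients are not prescribed a modulator.
- **The GM interval justifies the sample size.** Section 9.2 says that there was no formal calculation and that the number rests on feasibility. The tables illustrate precision.
- **Section 6 implies 48 participants in four cohorts.** Its 12 per cohort follows a sentence on the first three doses and placebo, and its 65 mg sentence gives no size.

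**Conclusion.** The point holds as an internal inconsistency. Section 6 is wrong for the current design: 12 per cohort and 36 in three cohorts, against 25. The N=10 factors and the 80% and 90% probabilities describe no planned arm. Relative to N=7, they show a factor of 1.402 instead of 1.548 at gCV 50%, and 80% instead of 68% for an AE of 15% incidence. The title and note of the stratum table overreach, and the text beside them is right. The missing GM interval for Cmax and AUC0-24 is not a departure of the SAP from the protocol; adding it is a free improvement that matches the outputs to the way Section 9.2 describes precision.

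Every tabulated value is correct for its N. The assessment takes the planned sizes at face value, although they are approximate, and makes no allowance for dropout because Section 9.2 states none. The factors rest on log-normal data with a t interval, the form that reproduces the plan's own tables.

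**What to change.** 1. **Protocol Section 6:** replace the 10 + 2 (12 per cohort) sentence with the allocation in Table 1 and Section 6.3, or with a cross-reference to them.
2. **Protocol Table 5, SAP Table 2 and the AE sentence in both documents:** delete the N=10 rows and probabilities. Keep the N=7 factors, 68% at 15% incidence, and 80% (81% if rounded) at 21%. Amend the introducing text to match.
3. **Protocol Table 6 and SAP Table 3:** restrict title and note to the CFTR modulator stratum only.
4. **Protocol 9.2 and SAP 4.2:** state that, at the planned n=2 per dose, non-modulator PK parameters are listed individually and summarised only when pooled across doses, since n=2 is below the SAP minimum of 3. Note that SAP 11.1.3 makes pooling conditional on dose proportionality.
5. **SAP 7.1:** add the 95% CI of the GM for Cmax and AUC0-24 to the PK-parameter summaries.

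The SAP changes can be made before database lock and the protocol changes at the next amendment. The cost is wording and one extra statistic in existing tables. The stated precision and detection figures will look less favourable. No participants, visits or samples are added.

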### **6.1. Investigational Product Administration**

Participants will be instructed to take 1 tablet of the study drug once a day, with water and with or without food, at approximately the same time of day each day in the morning. On the days of in-clinic visits the study drug will be administered by the study center staff. On Day 1 and Day 28 visits, participants will visit the study center and receive study drug after an 8-hour overnight fast. Except for Days 1 and 28, the study drug can be administered with or without food.

Details about the study drug are presented in [Table 2](#).

**Table 2: Investigational Product for Study INS1007-211**

Arm Name:	Placebo	Brensocatic			
Unit Dose:		10 mg	25 mg	40 mg	65 mg
Type:	Placebo	Drug	Drug	Drug	Drug
Formulation:	Tablet	Tablet	Tablet	Tablet	N/A a
Route:	Oral	Oral	Oral	Oral	Oral
Use:	Experimental	Experimental	Experimental	Experimental	Experimental
Manufacturer:	Insmed	Insmed	Insmed	Insmed	Insmed
Packaging and Labeling:	Study drug will be provided in HDPE bottles	Study drug will be provided in HDPE bottles	Study drug will be provided in HDPE bottles	Study drug will be provided in HDPE bottles	Study drug will be provided in HDPE bottles
Administered As:	One placebo tablet b	One 10-mg brensocatic tablet	One 25-mg brensocatic tablet	One 40-mg brensocatic tablet	One 25-mg brensocatic tablet AND one 40-mg brensocatic tablet

a Currently no 65 mg tablet exists. Participants who are randomized to brensocatic 65 mg will receive 2 bottles of study drug with different color labels on the bottles (1 bottle with brensocatic 25 mg tablets, 1 bottle with 40 mg tablets) and will take 1 tablet from each bottle on each dosing day.

b In the 65 mg dose cohort, participants randomly assigned to placebo will receive 2 bottles of study drug, both containing placebo tablets. To preserve the blind, participants will take 1 tablet from each bottle on each dosing day.

HDPE = high-density polyethylene, N/A = not applicable.

## 6.2. Preparation/Handling/Storage/Accountability

The Investigator or designee must confirm appropriate temperature conditions have been maintained during transit for all study drug received and any discrepancies are reported and resolved before use of the study drug. Study drug will be stored at temperatures as indicated on the label.

Only participants enrolled in the study may receive study drug and only authorized site staff may supply or administer study drug. All study drug must be stored in a secure, environmentally controlled, and monitored (manual or automated) area in accordance with the labeled storage conditions with access limited to the Investigator and authorized site staff.

The Investigator, institution, or the head of the medical institution (where applicable) is responsible for study drug accountability, reconciliation, and record maintenance (ie, receipt, reconciliation, and final disposition records).

Further guidance and information for the final disposition of unused study drugs are provided in the Study Pharmacy Manual.

### **6.3. Measures to Minimize Bias: Randomization and Blinding**

After meeting all inclusion criteria and none of the exclusion criteria, participants in each stratum (CFTR modulator and non-modulator) will be randomized by means of an IWRS in a 1:1:1 ratio to 1 of the first 3 dose cohorts (brensocatib 10, 25, or 40 mg); each cohort will enroll participants in a 5:1 ratio (active : placebo) for the CFTR modulator stratum. For the non-modulator stratum, approximately 6 participants will be randomized to active treatment in the first 3 dose cohorts and 1 participant will be assigned placebo. If there are no safety issues in these cohorts, a 65 mg dose cohort will be similarly randomized: 7 participants (5 participants CFTR modulator and 2 participants non-modulator stratum) in active treatment and 2 participants in placebo (1 participant each in the CFTR modulator and non-modulator strata), raising the total sample size from approximately 25 to 34 participants.

This is a single-blind study: participants are blinded to the study drug to which they are randomly assigned, as are the study center staff and the Investigator. Select Sponsor personnel comprising the SRC members and the Independent Clinical Pharmacologist are not blinded. The site will contact the IWRS prior to the start of study drug administration for each participant. The site will record the assigned study drug label number on the applicable electronic case report form (eCRF), if required.

Study personnel and participants are strongly discouraged from discussing any aspect of study treatment, with the exception of safety issues, to maintain treatment blinding and study integrity.

The IWRS will be programmed with blind-breaking instructions. In case of an emergency, the Investigator has the sole responsibility for determining whether unblinding of a participant's study drug assignment is warranted. Participant safety must always be the first consideration in making such a determination. If the Investigator decides that unblinding is warranted, the Investigator should make every effort to contact the Sponsor prior to unblinding a participant's study drug assignment unless this could delay emergency treatment of the participant. If a participant's study drug assignment is unblinded, the Sponsor must be notified within 24 hours after breaking the blind. The date and reason that the blind was broken must be recorded in the source documentation, as applicable.

